9.6.1.5 Expected adverse events

For this study, the applicable reference document is the most current version of the investigator's brochure (IB) for neladenoson bialanate.

Overview listings of frequent events that have occurred so far in the clinical development are shown in the current IB. If relevant new safety information is identified, the information will be integrated into an update of the IB and distributed to all participating sites.

The expectedness of AEs will be determined by the sponsor according to the applicable reference document and according to all local regulations.

9.6.1.6 Adverse events of special interest

Adverse events of special interest have to be reported to the sponsor along the timelines set for serious adverse events (even though they may not be classified as serious), i.e. within 24 hours of the investigator's awareness, as described in Section 9.6.1.4.

Adverse events of special interest are:

- Symptomatic bradycardia (HR < 50 bpm)
- Findings in ECG and / or AVIVO device as follows:
 - Mobitz type I AV-block leading to withdrawal or interruption of study drug
 - Mobitz type II AV block leading to withdrawal or interruption of study drug or leading to any change in therapy
 - Third degree AV blocks

9.6.2 Pregnancies

Females of childbearing potential are excluded from the study. However, the investigator must report to the sponsor any pregnancy occurring in a female study patient during her participation in this study. The outcome of the pregnancy should be followed up carefully, and any outcome of the mother and the child at delivery should be reported.

The child's health should be evaluated at birth.

For a pregnancy in the partner of a male study patient, all efforts will be made to obtain similar information on course and outcome, subject to the partner's consent.

For all reports, the forms provided are to be used. The investigator should submit them within the same timelines as an SAE.

9.6.3 Further safety

9.6.3.1 Laboratory evaluations

All laboratory evaluations will be done by central laboratory. Additional re-tests for liver monitoring (Section 9.6.3.6) will be done locally.

Hematology: erythrocytes, hemoglobin, hematocrit, MCV, MCH, MCHC, reticulocytes, leukocytes, differential blood count, platelets

Clinical chemistry: aspartate aminotransferase (AST), alanine aminotransferase (ALT), alkaline phosphatase (AP), gamma glutamyl transpeptidase (GGT), lactate dehydrogenase (LDH), creatine kinase (CK), amylase, lipase, glucose, cholesterol (HDL, LDL, total), triglycerides, creatinine, urea, uric acid, bilirubin, total protein, albumin, sodium, potassium, calcium, chloride, magnesium, anorganic phosphate

Coagulation: partial thromboplastin time (PTT), international normalized ratio (INR)

9.6.3.2 Physical examination

The physical examination (by means of inspection, palpation, auscultation) will be performed by a physician at the investigational site covering at least the organs of the cardiovascular, respiratory, abdominal and neurological system.

Abnormal physical examination findings are recorded either as medical history or as adverse events (see Section 9.6.1.1).

9.6.3.3 12-lead ECG

The standard 12-lead ECG will be evaluated by the investigator and the following parameters will be recorded in the eCRF: HR, PR interval, QRSD interval, QT interval (uncorrected). QTcB (QT interval frequency-corrected according to Bazett's formula) will also be calculated but will not be valid for evaluation. The frequency-corrected QT interval will be calculated by data management according to the formulas of both Bazett and Fridericia.

All ECGs recorded during the study will be evaluated by a physician. He / she will document the diagnosis(es) including an overall assessment of the findings and their clinical relevance. Any clinically relevant abnormality will be documented as an AE or SAE.

9.6.3.4 Blood pressure and heart rate

Heart rate and blood pressure (systolic and diastolic) will be measured by a member of the investigator's study team with the patient at rest.

9.6.3.5 AVIVO monitoring

This section was changed in Amendment 2, see Section 15.1 for details.

AVIVO Mobile Patient Management System will be used to monitor patients' cardiovascular status as part of the safety assessment. The cardiac monitoring device will be worn as specified in Section 9.1.

The system is intended to continuously measure, record and periodically transmit ECG data. The system can detect (but is not limited to) higher degree AV-blocks > I°, SVTs (e.g. atrial fibrillation [AF], atrial flutter, paroxysmal SVTs), ventricular ectopy, bradyarrhythmias, conduction disorders and heart rate variability. Included in the service is the monitoring center - an independent certified diagnostic testing center staffed with ECG-trained technicians who read through the transmitted events 24h/7d. An electrophysiologist is also on staff for interpretation of difficult rhythms. The system has achieved CE mark and has US FDA clearance.

Apart from safety assessments, also the patient's everyday physical activity (e.g. duration, intensity) will be tracked.

Details of the cardiac monitoring and the device to be worn by the patient will be outlined in a manual that will be provided to all participating centers.

9.6.3.6 Liver function monitoring

Any patient with an ALT or AST > 3 x ULN or alkaline phosphatase (AP) >2 x ULN must be re-tested as soon as possible but at the latest within 48-72 hours of the investigator becoming aware of the result. This re-testing and any subsequent testing based on elevated levels should include measurement of ALT, AST, total and direct bilirubin, and AP, and will be assessed by local laboratory. Every effort should be made to clarify the etiology of elevated levels. Patient management is at the discretion of the investigator but the treating physician may continue the study drug during retesting. Liver function test monitoring should be performed as above for all patients even if the study drug is interrupted until tested values have normalized or returned to patient's baseline. If close liver monitoring is not possible then the patient should discontinue study medication.

For ALT or AST > 3 x ULN concurrent with a total bilirubin > 2 x ULN, every effort should be made to clarify any possible underlying disease(s).

The frequency of liver function tests based on re-test values is shown in [Table 9-3](#).

Table 9-3: Liver function monitoring

ALT, AST or AP level at re-test	Frequency	Further notice
ALT or AST > 3 x ULN	2-3 times a week	Obtain details on liver related symptoms and exclude other causes of liver enzyme elevations
ALT or AST ≤ 3 x ULN	Once a week	Until return to normal or patient baseline levels
AP >2 x ULN	2-3 times a week	Obtain details on liver related symptoms and exclude other causes of liver enzyme elevations

Abbreviations: ALT = alanine aminotransferase; AP = alkaline phosphatase; AST = aspartate aminotransferase; ULN = upper limit of normal

Discontinuation of treatment should be considered if:

- ALT or AST > 8 x ULN
- ALT or AST > 5 x ULN for more than 2 weeks
- ALT or AST > 3 x ULN and (total bilirubin >2 x ULN or INR > 1.5)
- ALT or AST > 3 x ULN with the appearance of fatigue, nausea, vomiting, right upper quadrant pain or tenderness, fever, rash, and / or eosinophilia (> 5%)
- AP > 2 x ULN or ALT/AP < 2 for more than 2 weeks if other causes of cholestasis are excluded

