9.2.11 Unscheduled Visit

If a patient experiences an adverse event for which the investigator determines a follow-up site visit is necessary (either before the next scheduled study visit or during the Week 26 phone call), then the following assessments will be performed:

- Physical examination (Section 9.6.3.2)
- Weight measurement
- NYHA class assessment (Section 9.4.3.2)

- Blood pressure and heart rate measurement (Section 9.6.3.4)
- Adverse events assessment (Section 9.6.1.3)
- Concomitant medication collection and recording (Section 8.1)
- Blood sampling for safety (Section 9.6.3.1)

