9.6 Safety

9.6.1 Adverse events

9.6.1.1 Definitions

Definition of adverse event (AE)

In a clinical study, an AE is any untoward medical occurrence (i.e. any unfavorable and unintended sign [including abnormal laboratory findings], symptom or disease) in a patient or clinical investigation subject after providing written informed consent for participation in the study. Therefore, an AE may or may not be temporally or causally associated with the use of a medicinal (investigational) product.

A surgical procedure that was planned prior to the start of the study by any physician treating the patient should not be recorded as an AE (however, the condition for which the surgery is required may be an AE).

In the following differentiation between medical history and AEs, the term “condition” may include abnormal physical examination findings, symptoms, diseases, laboratory, or ECG findings.

- Conditions that started before signing of informed consent and for which no symptoms or treatment are present until signing of informed consent are recorded as medical history (e.g. seasonal allergy without acute complaints).
- Conditions that started before signing of informed consent and for which symptoms or treatment are present after signing of informed consent, at unchanged intensity, are recorded as medical history (e.g. allergic pollinosis).
- Conditions that started or deteriorated after signing of informed consent will be documented as adverse events.

Definition of serious adverse event (SAE)

An SAE is classified as any untoward medical occurrence that, at any dose, meets any of the following criteria (a – f):

- a. Results in death
- b. Is life-threatening

The term ‘life-threatening’ in the definition refers to an event in which the patient was at risk of death at the time of the event, it does not refer to an event which hypothetically might have caused death if it were more severe.

- c. Requires inpatient hospitalization or prolongation of existing hospitalization

A hospitalization or prolongation of hospitalization will not be regarded as an SAE if at least one of the following exceptions is met:

- The admission results in a hospital stay of less than 12 hours
- The admission is pre-planned

- (e.g. elective or scheduled surgery arranged prior to the start of the study; admission is part of the study procedures as described in Section 9.2)
- The admission is not associated with an AE (e.g. social hospitalization for purposes of respite care).

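### The liver re-test panel leaves out INR and a differential count, although two of the five advisory stopping criteria in the same section use them

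*Protocol*

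**What the plan says.** Protocol Section 9.6.3.6 requires a re-test when ALT or AST exceeds 3 x ULN or AP exceeds 2 x ULN. On content it says: "This re-testing and any subsequent testing based on elevated levels should include measurement of ALT, AST, total and direct bilirubin, and AP". These re-tests are done locally; Section 9.6.3.1 sends all other laboratory work to the central laboratory. Table 9-3 sets the frequency at two to three times a week while ALT or AST is above 3 x ULN.

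During this time "the treating physician may continue the study drug during retesting". The section then lists five situations in which stopping treatment should be considered. The third is "ALT or AST > 3 x ULN and (total bilirubin >2 x ULN or INR > 1.5", the INR limit being an alternative to the bilirubin limit. The fourth combines ALT or AST above 3 x ULN with any of several features, the list ending in "right upper quadrant pain or tenderness, fever, rash, and / or eosinophilia (> 5", where the figure is a percentage.

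The central safety panel in Section 9.6.3.1 includes both INR and a differential blood count. SAP Section 4.5.3 repeats that liver re-tests are local and adds no test to them.

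**The concern.** The panel and the stopping list stand in one section but do not match. The panel names direct bilirubin, which no stopping criterion uses, and omits two results that criteria do use. A site that follows the panel exactly, at the required frequency, can keep a patient on drug without seeing that the protocol's own prompt to consider stopping has been met.

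What is at stake is the safety of individual patients. The prompt matters most for a sustained rise between 3 and 5 x ULN. The list sets no time limit for such a rise, so only bilirubin, INR, the listed symptoms, eosinophilia and the AP criterion remain as prompts.

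**Working it through.** The plan gives no figure to reproduce. The check sets the texts side by side and works out the spacing of scheduled central samples.

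**Criteria against panel (Protocol 9.6.3.6)**

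| Advisory criterion | Results it uses | Outside the re-test panel |
|---|---|---|
| 1. ALT or AST > 8 x ULN | ALT, AST | none |
| 2. ALT or AST > 5 x ULN for more than 2 weeks | ALT, AST | none |
| 3. ALT or AST > 3 x ULN with bilirubin or INR raised | ALT, AST, total bilirubin, INR | INR |
| 4. ALT or AST > 3 x ULN with symptoms or eosinophilia | ALT, AST, symptoms, eosinophils | differential count |
| 5. AP or ALT/AP criterion | AP, ALT | none |

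Two of the five criteria have one branch that the panel cannot show. Neither is wholly unevaluable: criterion 3 can still be met through bilirubin, and criterion 4 through symptoms, which Table 9-3 asks sites to obtain.

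**When the two tests are next scheduled.** Inputs from Table 9-1: Week 4 = day 28 ± 2, Week 8 = day 56 ± 2, Week 12 = day 84 ± 2, Week 20 = day 140 ± 2. The shortest gap is the earliest next visit minus the latest trigger visit; the longest gap is the reverse.

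- Trigger at Week 4, next sample at Week 8: 54 − 30 = 24 days to 58 − 26 = 32 days.
- Trigger at Week 8, next sample at Week 12: 82 − 58 = 24 days to 86 − 54 = 32 days.
- Trigger at Week 12, next sample at Week 20: 138 − 86 = 52 days to 142 − 82 = 60 days. Section 9.2.8 puts the last dose on the day before that visit, so no scheduled sample falls before the last dose.

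These are visit spacings, not risks. At the Table 9-3 frequency, the nominal eight weeks from Week 12 to Week 20 could hold 8 × 2 = 16 to 8 × 3 = 24 local re-tests with neither test named.

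**What must coincide for the gap to matter.** All of the following are needed:

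- INR and eosinophils below their limits at the trigger, and one of them above its limit later;
- ALT or AST still above 3 x ULN, but not above 8 x ULN and not above 5 x ULN for more than two weeks;
- total bilirubin not above 2 x ULN, no listed symptom, and the AP criterion not met;
- drug continued, with no test added by the site and no unscheduled visit.

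**The case against.** The strongest reply is that the section works as a whole and leaves care to the physician.

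- The panel sentence sets a minimum, so a site may add tests, and a criterion that names INR or eosinophils tells the investigator to look at them.
- The section also says "Every effort should be made to clarify the etiology of elevated levels", and Table 9-3 asks sites to exclude other causes.
- A new enzyme rise can be an adverse event, since Section 9.6.1.1 covers "any unfavorable and unintended sign [including abnormal laboratory findings], symptom or disease". Section 9.2.11 then provides a visit with the full safety sample: "If a patient experiences an adverse event for which the investigator determines a follow-up site visit is necessary".
- There is a fallback: "If close liver monitoring is not possible then the patient should discontinue study medication".
- Patient management is expressly left to the investigator, the list is advisory, and the DMC reviews safety.

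These points are right and explain why the gap is small. None of them prescribes INR or a differential after the trigger. The duty to clarify the cause names no test. The unscheduled visit depends on the investigator's judgment. The fallback does not apply to a site that draws the named panel on schedule, because that site is monitoring closely as written. DMC review works at trial level and does not replace a blood result in one patient.

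Two smaller objections concern detail. A Week 0 trigger is also possible, because the baseline central sample is drawn before the first dose. With Week 0 at day 0 to 2, the next sample comes 26 − 2 = 24 to 30 − 0 = 30 days later, much the same interval as after Week 4 or 8. Second, the ALT or AST value is not known when the blood is drawn. If the condition is read as the latest known value, as Table 9-3 is, a patient who rises above 3 x ULN again would get the added tests from the following draw.

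**Conclusion.** The point holds at the lowest level of importance. The re-test panel cannot show one branch in each of two of the five advisory criteria, while the drug may be continued. The uncovered case is a rise in INR or eosinophils after the trigger in a patient who meets no other criterion and has no extra test.

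This assumes that the trigger comes from a central study sample, the only source the documents describe. The documents give no rate of liver triggers, so the number of affected patients is unknown; it is probably small. The primary analysis, the type I error and the power are unaffected.

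**What to change.** In Protocol Section 9.6.3.6, extend the re-test sentence after AP with: *and, while ALT or AST is > 3 x ULN, INR and a differential blood count*. Leave the discontinuation criteria unchanged and add no other rule.

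The cost is one sentence and two routine local assays on blood already being drawn, only in patients with ALT or AST above 3 x ULN. For a patient who stays above that level from Week 12 to Week 20, this could mean 16 to 24 repeats of each.

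The main downside is INR results that are high for non-hepatic reasons in patients on INR-raising anticoagulants. The documents do not say how many take them. SAP Section 6.1.4 lists anticoagulants as a medication of interest. Protocol Section 7.3 allows enrollment of atrial fibrillation patients to be stopped at 30% of the total, 0.30 × 384 = 115.2, or about 115 patients, which is not a firm cap. The share of these on an INR-raising drug is an assumption that could lie anywhere from none to all, and only those who also trigger would be re-tested. Such results need clinical judgment, as the existing INR criterion already does. Because the criterion only asks for discontinuation to be considered, and Section 6.4.1 discourages unnecessary withdrawal, no automatic stop follows.

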9.7 Other procedures and variables

Not applicable.

9.8 Appropriateness of procedures / measurements

All parameters, as well as the methods to measure them, are standard variables / methods in clinical studies and / or clinical practice. They are widely used and generally recognized as reliable, accurate, and relevant.

10. Statistical methods and determination of sample size

10.1 General considerations

Statistical analyses will be performed by or under the supervision of the sponsor's study statistician and the assigned study statistical analyst using statistical analysis system (SAS); the version used will be specified in the statistical analysis plan (SAP).

A general description of the statistical methods to be used to analyze efficacy and safety in this study is outlined below. A detailed SAP will be provided as a separate document that will be finalized and approved before database lock. The SAP will accommodate protocol amendments or unexpected issues in study execution or data that affect planned analyses and will provide more details on the analytical approaches, output tables and figures.

A meta-analysis of this study (15128) and of the study 17582 in patients with HFpEF, which is conducted at the same time, will be specified in a separate SAP.

10.2 Analysis sets

Documentation of protocol deviations and assignment of patients to analysis sets will be performed according to the sponsor's applicable Standard Operating Procedures and / or Operation Instructions.

The primary efficacy variables will be analyzed using the per-protocol set (PPS) and the full analysis set (FAS) for sensitivity analyses.

Data for all patients who signed informed consent but were not randomized will not be included in any statistical analyses except standard disposition tables and listings provided in the clinical study report (Screening failures and discontinued patients).

The statistical analysis sets are defined as follows:

Full analysis set (FAS)

The FAS population consists of all randomized unique patients. According to the ICH E9 guideline, this analysis set is as complete as possible and as close as possible to the intent-to-treat (ITT) ideal. Patients will be analyzed as randomized. The FAS will be used to display baseline characteristics and to display efficacy analyses.

Safety analysis set (SAF)

The SAF population consists of all randomized patients who received at least one dose of study medication after randomization. The SAF will be used to display safety analyses. For safety analyses, patients will be analyzed as treated.

Per-protocol set (PPS)

The PPS population consists of all FAS population patients without validity findings. Validity findings may include adherence and compliance issues and the violation of inclusion / exclusion criteria affecting efficacy evaluation. A list of potential validity findings will be provided in a separate protocol deviation document which will be finalized before database lock. The detailed definitions and the assignment of patients to this analysis set will be based on the validity review meeting. Patients will be analyzed as treated.

Pharmacokinetic analysis set (PKS)

The PKS population consists of all patients treated with neladenoson bialanate with at least 1 valid BAY 84-3174 plasma concentration and without protocol deviation that would interfere with the evaluation of the PK data.

10.3 Variables and planned statistical analyses

10.3.1 Variables

10.3.1.1 Primary efficacy variables

- Absolute change from baseline in left ventricular ejection fraction (LVEF; %) after 20 weeks measured by echocardiography.
- Absolute change from baseline in log-transformed NT-proBNP (pg/mL) after 20 weeks, i.e., log-transformed NT-proBNP at Week 20 minus log-transformed NT-proBNP at baseline

10.3.1.2 Secondary efficacy variables

Secondary efficacy variables across different domains are:

- Key echocardiographic parameters, measured values and absolute change from baseline at 20 weeks:
 - Left ventricular end-systolic volume (LVESV; mL)
 - Left ventricular end-diastolic volume (LVEDV; mL)
- High sensitivity troponin T (hs-TNT; ng/L), measured values (log transformed) and absolute / relative change from baseline at 20 weeks as a biomarker of myocardial injury
- CV mortality, HF hospitalization and urgent visits for HF as clinical outcomes

10.3.1.3 Other exploratory variables

This section was changed in Amendment 2, see Section 15.1 for details.

- Activity (duration, intensity) reported values and absolute change from baseline at 20 weeks
- Echocardiographic parameters, as described in Section 9.4.1, measured values and absolute / relative change from baseline at 20 weeks
- Left ventricular ejection fraction (LVEF; %), measured values, number of patients in whom absolute change from baseline after 20 weeks is > 5%

- Mandatory biomarkers, as described in Section 9.4.2, measured values and absolute / relative change from baseline at 20 weeks, including
 - NT-proBNP (pg/mL), measured values and relative change from baseline at 20 weeks to assess elevated filling pressures
 - UACR, cystatin-C, NGAL for the evaluation of kidney function
- KCCQ and EQ-5D-5L, as described in Section 9.4.4, measured values and absolute / relative change from baseline
- All-cause mortality, non-fatal myocardial infarction, non-fatal stroke
- Change in NYHA class

